6.2.1.1 Definition of Serious Adverse Event

A serious adverse event (SAE) is defined as any AE occurring at any dose that results in any of the following outcomes:

- a) Death - the death was an outcome of an AE.
- b) Life-threatening - the subject was at substantial risk of dying at the time of AE occurrence.
- c) Inpatient hospitalization or prolongation of existing hospitalization.
- d) A disability/incapacity - the AE resulted in a substantial disruption of a person's ability to conduct normal life functions, i.e., the AE resulted in a significant, persistent or permanent change, impairment, damage or disruption in the subject's body function/structure, physical activities and/or quality of life.
- e) A congenital anomaly in the offspring of a subject who received drug - it is suspected that exposure to study drug prior to conception or during pregnancy may have resulted in an adverse outcome in the child.
- f) Other SAEs: Important medical events that may not result in death, be life-threatening, or require hospitalization may be considered SAEs when, based upon appropriate medical judgment, they may jeopardize the subject or require medical or surgical intervention to prevent one of the outcomes listed in this definition. Examples of such medical events include allergic bronchospasm requiring intensive treatment in an emergency room or at home, blood dyscrasias or convulsions that do not result in inpatient hospitalization, or the development of drug dependency or drug abuse.

A distinction will be drawn between serious and severe AEs. Severity is a measure of intensity whereas seriousness is defined by the criteria above. An AE that is severe in intensity is not necessarily an SAE.

Clarifications:

- Any SAE that occurs after informed consent is signed will be reported.
- Life-threatening means that the subject is, in the view of the Investigator, at immediate risk of death from the event as it occurs. This definition does not include an event that, had it occurred in a more severe form, might have caused death.
- Hospitalization for elective treatment of a pre-existing condition that does not worsen during the study is not considered an AE.
- Complications that occur during hospitalization are AEs. If a complication prolongs hospitalization, the event is an SAE.
- Inpatient hospitalization means the subject has been formally admitted to a hospital for medical reasons (even if for less than 24 hours). However, this does not include the hospitalization due to the study treatment / procedure.
- Emergency room visit; the subject was seen and treated in the emergency room, and following treatment, subject was released. The Principle Investigator will assess if the event is considered a medically significant event.

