2.4.1 Potential Risks and Risk Mitigation

[figure not shown]
Since CT-P27 is a mixture of two monoclonal antibodies, typical AEs of monoclonal antibody therapy might be expected.

However, the overall risks of allergic reactions posed by CT-P27 are expected to be low based on the type of product (i.e., monoclonal antibodies that target an exogenous protein). This expectation was supported by available non-clinical and clinical data as outlined above (also see the Investigator's Brochure).

Based on non-clinical data, free CT-P22 and CT-P23 are not expected to cause unwanted immune system activation via Fc γ RIIIa binding on effector immune system cells. Therefore, ADE is not expected. In the limited clinical experience with CT-P27, there were no anaphylactic reactions and only a few infusion-related TEAEs (headache, rash) were reported. Furthermore, the immunogenicity against CT-P27 components appeared to be extremely low.

To minimize the effects of an immune- or infusion-related reaction, study drug will be administered slowly, over a 90-minute period (\pm 15 minutes). Emergency drugs and equipment suitable for assistance during anaphylactic reactions will be available during infusion with study drug.

This study will be performed in compliance with International Council for Harmonisation (ICH) Good Clinical Practice (GCP) guidelines and applicable local regulatory requirements.

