A PK sub-study will be performed on the subjects who signed informed consent to participate in a PK sub-study. Of total number of subjects to be enrolled, approximately 53 subjects (20 subjects per CT-P27 treatment groups and 13 subjects in placebo group) will be included in the Subgroup (PK) Cohort, and additional PK samples from the subjects in this cohort will be collected according to the schedule of assessments. A schematic diagram for the study cohorts is presented in [Figure 3](#).

Figure 3 Schematic Diagram for the Study Cohorts

Subjects may be admitted in a hospital from Day 1 (before study drug administration) to Day 3 (after completion of the 48 hours assessments) if it is deemed necessary upon the judgement of the investigator.

Study visits:

- Subjects who are included in Whole Study Cohort and are hospitalized: 4 planned study visits
- Subjects who are included in Whole Study Cohort but are not hospitalized: 6 planned study visits
- Subjects who are included in the Subgroup (PK) Cohort and are hospitalized: 7 planned study visits
- Subjects who are included in the Subgroup (PK) Cohort but are not hospitalized: 9 planned study visits

Efficacy Assessment:

The completion of the Influenza Intensity and Impact Questionnaire (Flu-iiQ™) (see [Appendix 2](#) for a copy of the questionnaire and [Section 6.1.1.1](#) for details describing the questionnaire) and the recording of body temperature will take place at screening for baseline assessments. After study drug administration, subjects will be instructed to complete the Flu-iiQ™ and the body temperature in the diary twice a day (at approximately 12-hour intervals) from Day 1 to Day 8 (in the morning [between 6 and 10 AM, approximately] and in the evening [between 6

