6.2.1.6 Reporting of a Serious Adverse Event and a SUSAR

Any SAE (including death due to any cause and SUSARs) that occurs during this study, whether or not related to the study drug, must be reported immediately (within 24 hours of the study site's knowledge of the event) by E-mail, telephone or fax to the Sponsor's authorized representative at the following table.

█	█	█
█	█	█

The report will contain as much available information as possible concerning the SAE to enable the Sponsor (or an authorized representative) to file a report, which satisfies regulatory reporting requirements. If SAE follow up is reported via eCRF, a completed, separate SAE follow up notification should be sent to Sponsor (or CRO) by fax or email within 24 hours of the study site's awareness of the event.

The information in the report of the SAE must include at least the following:

- Name, address, and telephone number of the reporting Investigator.
- Investigational product and study code.
- Subject identification number, initials, sex, and date of birth or year of birth.
- Description of the AE/SAE, measures taken, and outcome.
- Preliminary classification of causal relationship by the Investigator.

If SAE follow up reporting is performed using a SAE report form, its original contents should be appropriately reflected on the relevant page of the eCRF.

Any SAEs reported spontaneously after the last study visit on Day 110 (or after EOS visit) will only be reported if the Investigator suspects a causal relationship to the study treatment.

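### The SAE clarification on hospitalization is over-broad: read literally, it takes a new admission for an AE caused by the study drug or a study procedure out of the hospitalization criterion

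*Protocol*

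**What the plan says.** Protocol Section 6.2.1.1 lists, as criterion (c) for a serious adverse event, "Inpatient hospitalization or prolongation of existing hospitalization". Its clarifications then define the term: "Inpatient hospitalization means the subject has been formally admitted to a hospital for medical reasons (even if for less than 24 hours"). The next sentence reads: "However, this does not include the hospitalization due to the study treatment / procedure". No further condition is attached. The sentence does not mention planned stays, the absence of an adverse event, or a time window.

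Other parts of the plan that bear on it:

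- **Protocol 4.1** offers an optional stay: "Subjects may be admitted in a hospital from Day 1 (before study drug administration) to Day 3 (after completion of the 48 hours assessments"). Whether to use it is left to the investigator. The number of planned visits depends on whether this stay is used (4 against 6 in the whole study cohort, 7 against 9 in the PK cohort).
- **Protocol 6.2.1** says that a situation with no untoward medical occurrence, such as a convenience admission, is not an AE, and that complications of a procedure are AEs.
- **Protocol 6.2.1.1** also says that a complication that prolongs a hospital stay is an SAE.
- **Protocol 6.2.1.2, 6.2.1.6 and 6.2.1.7** make expedited reporting depend on SAE status: a SUSAR has to be a treatment-related SAE, sites report SAEs within 24 hours, and SUSARs go to authorities within 7 or 15 days.
- **SAP 12.1** restates the SAE definition with hospitalization and without the exclusion.

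**The concern.** In ordinary language, an admission for a reaction to the infusion is a hospitalization due to the study treatment. A site that follows the clarification to the letter could therefore decide that such an admission does not meet criterion (c). These are the admissions that expedited safety reporting most needs to catch.

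The protocol itself anticipates reactions of this kind. Section 2.4.1 says "To minimize the effects of an immune- or infusion-related reaction, study drug will be administered slowly", and Section 6.2.7 schedules hypersensitivity checks on Day 1. If the event is not classed as serious, the 24-hour report is not triggered, and the SUSAR question does not arise because it presupposes an SAE. Treatment-emergent SAEs are also a listed secondary safety endpoint (Protocol 8.2.3).

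**Working it through.** No arithmetic applies, and the plan gives no figure to reproduce. The check is to ask, for each type of hospital stay, whether the exclusion changes the classification.

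| Type of stay | Criterion (c) and Section 6.2.1 without the sentence | With the sentence read literally |
|---|---|---|
| Planned study stay, no AE | No AE, so not an SAE | Not an SAE |
| Planned study stay, extended because of a complication | SAE (prolongation rule) | SAE (prolongation rule still stands) |
| New admission for an AE unrelated to drug or procedure | SAE | SAE |
| New admission for an AE caused by drug or procedure | SAE | Not under (c); an SAE only if another criterion applies |

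1. **The planned stay does not need the sentence.** Only an AE can be an SAE. Section 6.2.1 already keeps a stay with no untoward occurrence out of the AE definition, and the definition of inpatient hospitalization already requires a medical reason.

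2. **Only the last row changes.** The sentence alters a classification only where an AE caused by the drug or a procedure has led to a new admission. That also fits poorly with Section 6.2.1, which counts complications of a procedure as AEs.

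3. **What is left for the last row.** Death, life-threatening and disability cover the gravest cases. The prolongation rule helps only a subject already in hospital. The important-medical-event criterion (f) can apply, but it is permissive and rests on judgement. A new admission for a drug reaction that is not life-threatening loses its one objective criterion.

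4. **The SAP does not repair it.** SAP 12.1 omits the exclusion, so the two documents define an SAE differently. However, the SAP takes the serious/not serious flag from the eCRF. An event that a site recorded as non-serious under the protocol stays non-serious in the treatment-emergent SAE table (SAP 12.1.2). The SAP definition also has no effect on what a site reports within 24 hours.

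**The case against.** The best defence is the context. The sentence directly follows a definition built on admission for medical reasons. Set against that, a stay due to the study treatment or procedure can naturally mean a stay to give the treatment or carry out the procedures, and the protocol provides for such a stay. On that reading an admission to treat a reaction is for a medical reason and remains an SAE. Clarifications are often redundant, so redundancy alone does not prove that the literal reading was meant. This stands as far as intent goes: it is loose drafting, and many investigators would report such an admission anyway. It does not settle how a site must apply the words, because nothing in the text chooses between the two readings.

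The safeguards are also real. Criterion (f) gives allergic bronchospasm needing intensive emergency-room treatment as an example. All AEs are recorded whatever their seriousness (Protocol 6.2.1.5). Infusion-related and anaphylactic TEAEs have their own table and listing (SAP 12.1.1.2), and TEAEs of Grade 3 or higher have a separate summary (SAP 12.1.1). Many affected events would stay visible in the final safety analysis. Those summaries do not replace expedited reporting.

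A reader might infer four stronger points that the documents do not support:

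- **That drug-caused admissions are never SAEs.** The other criteria and the prolongation rule remain in force.
- **That Section 4.1 widens the gap by allowing any admission from Day 1 to Day 3.** It describes a stay that starts before dosing and ends after the 48-hour assessments. A subject dosed as an outpatient and admitted later that day for a reaction does not fit that description, so the problem rests on Section 6.2.1.1 alone.
- **That the treatment-emergent SAE comparison is biased towards no difference.** This would need sites to adopt the literal reading and also not to use criterion (f). Neither is shown.
- **That the loss can be put as a percentage.** No frequency of such admissions is given, so any percentage would estimate nothing.

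**Conclusion.** The clarification is over-broad. Applied as written, it removes a new admission for an AE caused by the study drug or a study procedure from criterion (c), although the likely aim was only to set aside planned study stays. What is at risk is the 24-hour report and SUSAR assessment of such an event at a site that takes the sentence literally and does not classify the event as serious under another criterion. The protocol and SAP definitions also disagree.

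The size cannot be quantified from the documents. The conclusion rests on the plain wording and on the absence of any limiting condition; it assumes nothing about how often such admissions occur or how many sites would read the sentence that way. The primary efficacy analysis is not affected. The point is worth acting on because expedited reporting works case by case and the repair is nearly free.

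**What to change.** Replace the sentence in Protocol 6.2.1.1 with wording to this effect: the hospitalization criterion does not cover a stay arranged before the infusion solely for study drug administration, observation or sampling, when no AE led to it; any admission, or any extension of such a stay, to evaluate or treat an AE meets the criterion, including an AE caused by the study drug or a study procedure.

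Bring SAP 12.1 into line by restating the same definition or referring to the amended protocol section. This keeps the probable purpose of the exclusion and agrees with Protocol 6.2.1.

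The cost is a short protocol amendment, a matching SAP edit and a reminder to sites. The downside is that the reported SAE count may be slightly higher.

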6.2.1.2 Definition of Suspected Unexpected Serious Adverse Reaction (SUSAR)

An adverse reaction, the nature or severity of which is not consistent with the applicable product information (e.g., for applicable product information, include the Investigator's Brochure for an unapproved investigational product or the package insert/summary of product characteristics for an approved product). Therefore, if a treatment-related SAE occurs and it was not mentioned in the applicable product information, then it will be reported as a SUSAR (see [Section 6.2.1.6](#)).

6.2.1.3 Lack of Efficacy as an AE or SAE

Lack of efficacy is not considered as an AE in clinical trials. However, disease-related complications will be reported as an AE.

6.2.1.4 Evaluation of AEs

Each AE is to be evaluated for duration, severity, seriousness, and causal relationship to the investigational drug. The action taken and the outcome must also be recorded.

Seriousness

The event will be evaluated to determine if it meets the criteria for an SAE, as described in [Section 6.2.1.1](#).

Severity/Intensity

The severity of the AE will be characterized according to the following criteria based on the Common Terminology Criteria for Adverse Events (CTCAE) v4.03:

- Grade 1 Mild; asymptomatic or mild symptoms; clinical or diagnostic observations only; intervention not indicated.
- Grade 2 Moderate; minimal, local or noninvasive intervention indicated; limiting age-appropriate activities of daily living.
- Grade 3 Severe or medically significant but not immediately life-threatening; hospitalization or prolongation of hospitalization indicated; disabling; limiting self-care activities of daily living.
- Grade 4 Life-threatening consequences; urgent intervention indicated.
- Grade 5 Death related to AE.

When evaluating an AE that recurs over time (for example, a specific AE reported multiple times in the diary), the Investigator will review the AE for changes in severity over the time period being assessed. The most severe grade will be assigned to that AE.

Relationship/Causality

The Investigator will assess the causality/relationship between the study drug and the AE and record that assessment in the eCRF. One of the following categories will be selected based on medical judgment, considering the definition below and all contributing factors. However, for the summarization of data, all categories other than unrelated will be considered as related to study drug.

- Definite: A clinical event, including laboratory test abnormality, occurring in a plausible time relationship to drug administration, and which cannot be explained by concurrent disease or other drugs or chemicals. The response to withdrawal of the drug (dechallenge) will be clinically plausible. The event must be definitive pharmacologically or phenomenologically, using a satisfactory rechallenge procedure if necessary.
- Possible: The relationship suggests that the association of the AE with the study drug is unknown; however, the AE is not reasonably supported by other conditions.
- Probable: The relationship suggests that a reasonable temporal sequence of the AE with drug administration exists and, in the Investigator's clinical judgment, it is likely that a

causal relationship exists between the drug administration and the AE, and other conditions (concurrent illness, progression, or expression of disease state or concomitant medication reactions) do not appear to explain the AE.

- Unrelated: There is not a reasonable possibility that the study drug caused the AE.
- Not Assessable: All efforts will be made to classify the AE according to the above categories. The category “unknown” (unable to judge) may be used only if the causality is not assessable, (e.g., because of insufficient evidence, conflicting evidence, conflicting data, or poor documentation).

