6.2.1.5 Recording and Follow-up of AEs and SAEs

All AEs/SAEs, regardless of the relationship to study drug, will be assessed and recorded from the date the ICF is signed until Day 110 (approximately 5 half-lives) after the administration of study drug.

Subjects will be trained on the recording of AEs into their diary up to Day 8, and this information will be transferred to the eCRF after verification of the investigator. If there is any AE after Day 8, subjects will be instructed to contact the Principal Investigator or sub-Investigator at any time. Any AE occurring during the study must be documented in the subject’s medical records, in accordance with the Investigator’s normal clinical practice, and on the AE page of the eCRF. SAEs that occur during the study must be documented in the subject’s medical record and on the SAE page of the eCRF. Serious adverse event reporting is discussed in [Section 6.2.1.6](#).

A separate set of SAE pages will be used for each SAE. However, if at the time of initial reporting multiple SAEs that are temporally and/or clinically related are present, they may be reported on the same SAE page.

All AEs/SAEs will be recorded individually in the study subject’s own words (verbatim) unless, in the opinion of the Investigator, the AEs/SAEs constitute components of a recognized condition, disease, or symptom. The Investigator will attempt to establish a diagnosis of the event based on signs, symptoms, and/or other clinical information. In such cases, the diagnosis will be documented as the AE and/or SAE rather than the individual signs/symptoms.

If a clinically significant abnormal laboratory finding or other abnormal test result meets the definition of an AE or SAE, then the AE eCRF page or SAE eCRF page must be completed, as appropriate. A diagnosis (if known), or clinical signs and symptoms (if diagnosis is unknown), rather than the clinically significant abnormal laboratory finding or test result, will be entered on the AE or SAE eCRF page. If no diagnosis is known and clinical signs and symptoms are not present, then the abnormal finding will be recorded.

Treatment-related AEs and treatment-related SAEs will be followed up until resolution or medical condition stabilizes.

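### All three graded causality categories rule out another explanation, so an AE that either study drug or influenza could have caused fits only the last-resort Not Assessable category

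*Protocol*

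**What the plan says.** Protocol 6.2.1.4 (Relationship/Causality) gives five categories. The investigator chooses one by medical judgment, taking the definitions and all contributing factors into account.

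- *Definite* is for an event "which cannot be explained by concurrent disease or other drugs or chemicals".
- *Probable* requires that "other conditions (concurrent illness, progression, or expression of disease state or concomitant medication reactions) do not appear to explain the AE".
- *Possible* is for the case where "the association of the AE with the study drug is unknown; however, the AE is not reasonably supported by other conditions".
- *Unrelated* reads: "There is not a reasonable possibility that the study drug caused the AE".
- *Not Assessable* comes last, after an instruction to make every effort to use the others. The text then calls it unknown and says that it "may be used only if the causality is not assessable, (e.g., because of insufficient evidence, conflicting evidence, conflicting data, or poor documentation").

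For data summaries, 6.2.1.4 counts every category except *Unrelated* as related. SAP 12.1 repeats this and names *Not Assessable* among the related categories.

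Two other rules use relatedness. Protocol 6.2.1.2 says that "if a treatment-related SAE occurs and it was not mentioned in the applicable product information, then it will be reported as a SUSAR". Protocol 6.2.1.5 says that "Treatment-related AEs and treatment-related SAEs will be followed up until resolution or medical condition stabilizes". Neither section mentions *Not Assessable*.

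**The concern.** A causality scale normally keeps its weakest positive grade for events with two credible causes. Here that grade carries the same exclusion as the stronger ones. The trial enrols people with acute influenza, so the disease under study is a competing explanation for some of the reactions the drug might cause. Headache is an example: it is among the constitutional symptoms in Protocol 4.3.1, and Protocol 2.4.1 says of earlier experience with CT-P27 that "only a few infusion-related TEAEs (headache, rash) were reported".

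Three outputs are at stake: the related-TEAE summary (SAP 12.1.1, Table 14.3.1.3), SUSAR status, and the general rule on following events to resolution or stabilisation. If investigators apply the definitions as written, some drug reactions could be graded *Unrelated* because influenza also explains them, or graded differently from site to site.

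**Working it through.** No arithmetic applies. The check takes an AE for which study drug and influenza are both plausible causes and tests it against each definition.

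| Category | What it demands about causes | Related in summaries? | Fits the dual-cause AE? |
|---|---|---|---|
| Definite | No explanation by concurrent disease or other drugs | Yes | No |
| Probable | Other conditions do not seem to account for it | Yes | No |
| Possible | Other conditions do not reasonably support it | Yes | No |
| Unrelated | A drug cause is not reasonably possible | No | No |
| Not Assessable | No exclusion; causality cannot be assessed | Yes | Only if the ambiguity is read as insufficient or conflicting evidence |

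All 3 of the 3 graded categories contain an alternative-cause exclusion. In summaries, 4 of the 5 categories count as related, and the fourth, *Not Assessable*, is the only one without the exclusion.

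Next, which events reach this scale? Protocol 6.2.1 does not treat symptoms of the disease under study as AEs unless they exceed what would be expected for that subject. Ordinary influenza symptoms are captured on the Flu-iiQ and in the temperature diary, and never reach causality grading. Three groups do or may reach it:

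1. Symptoms judged worse or more frequent than expected (6.2.1).
2. Influenza complications. Section 6.2.1.3 makes disease-related complications AEs. Section 6.1.5 has secondary complications classed as AEs or as adverse drug reactions according to the causality assessment. Yet an event already called a complication of influenza has influenza as an explanation, so read literally no graded category is open to it. Section 6.1.5 therefore asks for a distinction that the graded definitions in 6.2.1.4 do not let the investigator make.
3. Influenza-like events recorded as AEs in subjects with suspicious ADE. Section 6.2.5 defines suspicious ADE as symptoms unresolved or worsened up to Day 8, or a later influenza-like illness. ADE is named in the secondary objective (3.2), and this potential harm resembles influenza by its definition. SAP 12.9 counts these subjects separately and the DSMB reviews the cases (6.2.5), but neither step sets the causality grade of the AE.

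Finally, what follows from each choice for such an event?

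- *Unrelated*: not in the related-TEAE table, not a SUSAR, and not covered by the follow-up rule in 6.2.1.5.
- *Not Assessable*: in the related-TEAE table. SUSAR status and follow-up are undetermined, because the counting rule in 6.2.1.4 is stated for summaries only.

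**The case against.** The strongest reply is that a related category does exist. *Not Assessable* counts as related, and conflicting evidence is one of its stated grounds. This stands against any inference that such a reaction has no related category at all; the documents do not support that reading. It does not remove the problem. The category is a last resort, its examples describe deficient or conflicting information, and a well-documented event with two credible causes is an awkward fit.

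A reader might also infer that a headache after infusion can never be graded as related. That goes too far. The category is chosen by medical judgment, timing can count, and a headache that qualifies as an AE because it exceeds what influenza would be expected to produce may reasonably be graded *Possible*. But exceeding expectation does not rule influenza out, and the argument does not reach complications.

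Nor do the documents support saying that every subject has influenza, or that dual-cause events are the most common situation. Protocol 4.3.3 keeps subjects who are negative on confirmatory testing, and 8.1 assumes that 90% belong to the infected population. AEs are collected to Day 110, while Protocol 2.1 says that most people recover within two weeks. The overlap lies mainly in the acute illness, apart from later influenza-like illness.

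Several safeguards hold whatever the grade:

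- Total TEAE counts by arm do not depend on causality (SAP 12.1.1), although the breakdown by relationship does.
- Infusion reactions have their own eCRF question and table (SAP 12.1.1.2, Table 14.3.1.7).
- All SAEs go to the sponsor within 24 hours, related or not (Protocol 6.2.1.6).
- Severe infusion-related reactions (5.4) and clinically significant laboratory results (6.2.4) are followed without a causality condition.

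These limit the consequences. They do not settle related-TEAE counts, SUSAR classification or the general follow-up rule.

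**Conclusion.** The point holds in a limited form. The definitions of *Definite*, *Probable* and *Possible* all exclude a competing explanation, and *Unrelated* excludes a plausible drug cause. A qualifying AE with both causes plausible is left with *Not Assessable*, whose treatment-related status is defined for summaries only. This is a defect in a stated rule, not a missing detail.

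The likely effect is an inconsistent or low count of related TEAEs, and inconsistent SUSAR classification and therefore inconsistent use of the 7- and 15-day reporting limits in Protocol 6.2.1.7. The all-causality comparison with placebo is not affected. No figure can be put on the effect, because the documents give neither a rate for such events nor any indication of how sites would divide them. The conclusion rests on investigators giving weight to the written definitions, as 6.2.1.4 tells them to; those who set the wording aside would avoid the problem. It merits correction because the change is small and Protocol 6.1.5, 6.2.1.2 and 6.2.1.5 all depend on this scale.

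**What to change.** In Protocol 6.2.1.4:

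1. Redefine *Possible* as an AE with a reasonable time relationship to study drug that the drug could have caused, although concurrent disease (including influenza) or other drugs could also explain it. *Definite*, *Probable* and *Unrelated* can stay as they are.
2. State whether *Not Assessable* counts as treatment-related for SUSAR status (6.2.1.2) and for follow-up (6.2.1.5).
3. Use one label for that category throughout, since the text now gives it two.

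Put the same wording in the eCRF completion guideline and send sites a short memo. The SAP rule on what counts as related needs no change.

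The cost is a sentence or two in the protocol, the guideline edit and the memo. The downside is that somewhat more AEs will be coded as related. Because causality is assessed under the double blind (Protocol 5.8), this should not favour either the CT-P27 groups or placebo. If events have already been graded under the present definitions, the study report should say which definition applied to them.
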